3. STUDY DESIGN

3.1 DESCRIPTION OF THE STUDY

Study Period A: This is a prospective, randomized, double-blind, placebo-controlled, parallel-group study of crenezumab versus placebo in individuals who carry the *PSEN1 E280A* autosomal-dominant, mutation-causing EOAD and do not meet criteria for MCI due to AD (Albert et al. 2011) or dementia due to AD (McKhann et al. 2011) and are, thus, in a preclinical phase of AD (Sperling et al. 2011b). The study also incorporates administration of placebo to individuals who are not *PSEN1 E280A* autosomal-dominant mutation carriers. This efficacy and safety study will be conducted at a single primary site and approximately three satellite sites in Colombia.

In the Colombian study, *PSEN1 E280A* autosomal-dominant mutation carriers who meet study eligibility criteria will be randomized in a 1:1 ratio to one of two treatment groups: crenezumab or placebo. Crenezumab will be administered either SC (720 mg Q2W) or IV (60 mg/kg Q4W). Matching placebo will be administered by the same routes at the same frequencies. The switch to the higher IV dose

(approximately 4-fold higher exposure to crenezumab) will be optional. Participants may decide whether to change from the current SC dosing to the IV dose; however, once IV dosing in a given participant has occurred, it is not intended for a participant to switch back to the lower SC dose. In order to maintain genotype blind and to have a genetic kindred control, a cohort of *PSEN1 E280A* mutation non-carrier kindred family members will also be enrolled in the study and dosed only with placebo.

The study includes three arms with approximately 100 participants per arm; two arms of participants with a *PSEN1 E280A* mutation randomized in a 1:1 ratio to crenezumab or placebo and a third arm of non-carriers randomized to placebo. Participants will receive the randomized treatment until the final participant has reached their final treatment visit at 260 weeks (see [Figure 1](#)).

[figure not shown]

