remain blinded to study drug treatment assignment during the blinded treatment period in Study Period A as well as during the Study Period B (see Section 3.8 for details on blinding). Following the *data snapshot date* for the Study Period A *primary readout*, selected members of the Sponsor team may become unblinded for the purpose of analysis and interpretation of Study Period A data. *During Study Period B, after the results of Study Period A are available, study participants may choose to learn their mutation carrier status (see Sections 3.8 and 3.9 for additional information).*

Participants will have the option to receive the same dose (720 mg SC Q2W or 60 mg/kg IV Q4W) they were receiving at the end of the Study GN28352 *Period A* or switch to the higher dose of 60 mg/kg IV Q4W if they have not already switched. See Section 3.2.2 for rationale for crenezumab dosage.

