3.5.2.2 Management of Amyloid-Related Imaging Abnormalities

Amyloid-Related Imaging Abnormalities—Edema/Effusion (ARIA-E)

The following rules for the management of MRI-related findings apply for ARIA-E:

- Asymptomatic ARIA-E with Size < 4 BGTS (Barkhof et al. 2013)
 - Continue study drug at the same dose (i.e., 60 mg/kg crenezumab)
 - Repeat MRI 4 weeks later
 - If ARIA-E is stable or decreased, continue study drug and monthly MRI monitoring until event resolves. Once ARIA-E completely resolves, conduct MRI monitoring as per study flowchart.
 - If ARIA-E increases (BGTS ≥ 4) or symptoms develop, see the rules below.
- Symptomatic ARIA-E (of any size) or asymptomatic ARIA-E with size ≥ 4 BGTS:
 - Temporarily interrupt study drug and implement monthly MRI monitoring
 - Once symptoms and ARIA-E resolve, reintroduce study drug and perform an MRI after 4 weeks of dosing. If no new MRI abnormality is detected, resume MRI monitoring as per the study flowchart.
- For any new onset of ARIA-E:
 - Treat the same as the first event, on the basis of symptoms and BGTS

- If a participant is diagnosed with 3 recurrent, symptomatic ARIA-E events or exacerbations of previous events, permanently discontinue the study drug
- Implement monthly MRI monitoring until resolution of both symptoms and ARIA-E
- As per the protocol, maintain the participant in the study until study end and perform assessments as per the study flowcharts

Amyloid-Related Imaging Abnormalities–Hemosiderin Deposition (ARIA-H)

The following dose adjustments and discontinuation rules for MRI-related findings will apply to ARIA-H:

- Dose reduction: Participants who develop >8 ARIA-H cumulatively will receive a lower dose of the study drug. Cumulative is the sum of ARIA-H at baseline and newly detected ARIA-H during the study.
- Study drug discontinuation: Participants who develop >10 ARIA-H cumulatively will be permanently discontinued from the study drug. Cumulative is the sum of ARIA-H at baseline and newly detected ARIA-H during the study.

The Sponsor believes that the above rules, coupled with frequent MRI monitoring and collection of CNS symptoms, will ensure safety while trying to maximize benefit for the participants.

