4.3.1.2 Dosage, Administration, and Storage

Crenezumab will be administered to participants under close medical supervision in a setting with access to appropriate emergency equipment and staff who are trained to monitor and respond to medical emergencies.

Subcutaneous dosing: Crenezumab has been formulated for SC injection, and no dilution of the drug product or placebo is necessary prior to administration.

Administration: Study drug will be administered SC into the back of the arm, the thigh, or the abdomen via polypropylene syringe. The total volume of drug will be 2×2.0 mL (2×360 mg), administered in 2 injections. Vital signs will be measured prior to the injection. Study participants will be observed for a minimum of 30 minutes following the first 4 administrations of study drug (180 mg/mL formulation) and for a minimum of 15 minutes subsequently.

Intravenous dosing: IV infusions will be administered by appropriately trained staff in the clinic.

The IV drug or placebo will be prepared and infused from the IV bag by infusion pump. The bag size, drug preparation, and infusion rates are all described in the pharmacy manual guidance. For the IV dose calculation, the participant's weight should be used. If the current weight changes by $\geq 10\%$ from the previous reference weight, the current weight should become the new reference weight for subsequent dosing. If the participant's weight changes again by $\geq 10\%$ from the reference weight, the IV dose should again be recalculated. See the pharmacy manual for further information.

Administration: Vital signs will be measured just prior to study drug administration, at the end of the IV infusion, and ≥ 60 minutes after the end of the infusion.

Study participants will be observed for a minimum of 60 minutes following IV administration of study drug.

Participants who experience a moderate IRR (e.g., fever or chills) should have the infusion stopped immediately and should receive aggressive symptomatic treatment. The infusion should not be restarted before all symptoms have disappeared, and then it should be restarted at half the initial rate.

Participants who experience serious or severe hypersensitivity reactions (e.g., hypotension, mucosal involvement) should not receive additional study drug. In addition, in any case of anaphylaxis, anaphylactoid reaction, serious or severe hypersensitivity reaction, ADA and concurrent PK samples should be collected as close

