4.3.1.3 Dosage Modification

Participants with a serious, life-threatening adverse event or who meet the criteria for dose discontinuation in Section 3.5.4 must not receive additional doses of study drug (crenezumab or placebo) but will be invited to, and should, remain in the study and complete study assessments per the protocol (see the study flowcharts in [Appendix 1](#), [Appendix 2](#), [Appendix 3](#), and [Appendix 4](#)) if this is deemed to be safe and clinically appropriate by the investigator.

Participants who experience serious or severe hypersensitivity reactions (e.g., hypotension, mucosal involvement) should not receive additional study drug. In addition, in any case of anaphylaxis, anaphylactoid reaction, serious or severe hypersensitivity reaction, ADA and concurrent PK samples should be collected as close as possible to the event, and then at 4 and 16 weeks postdose (see the study flowcharts for further details).

Study drug will be held for participants experiencing other clinically significant neurologic deterioration attributed to the study drug, as judged by the investigator, or other adverse events (including ARIA-E is associated with neurologic symptoms or if BGTS >4, without symptoms). Status will be assessed by MRI follow-up every 4 weeks until symptoms and ARIA-E resolve. Reintroduce study drug and perform an MRI scan after 4 weeks of dosing. If no new ARIA-E is detected, resume MRI monitoring as per study flowcharts.

Any new onset of ARIA-E: Treat the same as the first event, on the basis of symptoms and BGTS. However, in the case where a participant is diagnosed with three recurrent, symptomatic ARIA-E events or exacerbations of previous events, permanently discontinue the study drug. Implement monthly MRI monitoring until resolution of both symptoms and ARIA-E.

ARIA-H

Dose reduction: Participants who develop >8 ARIA-H cumulatively will receive a lower dose of the study drug. Cumulative is the sum of ARIA-H at baseline and newly detected ARIA-H during the study.

Study drug discontinuation: Participants who develop >10 ARIA-H deposition cumulatively will be permanently discontinued from the study drug. Cumulative is the sum of ARIA-H at baseline and newly detected ARIA-H during the study.

The participant will be invited to remain in the study and complete study assessments per the protocol. All such cases should be discussed with the Medical Monitor.

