5.3.5 Supplementary Analyses for Primary Endpoints

The following supplementary analyses will be performed for the primary endpoints to provide further understanding of the treatment effect.

- Analysis investigating efficacy in SC crenezumab versus efficacy in IV crenezumab: In this analysis, the treatment effect will be assumed to be different between the 2 administration periods. This analysis intends to gain insight on the impact of dose on the treatment effect. Since the IV dose is approximately 4-fold higher than the SC dose, we can use the administration method as a proxy for the dose. In this analysis, the change in administration method is assumed to change the population-level outcome trajectory for participants in the placebo group. For participants in the crenezumab group, the population-level outcome trajectory will also change once an administration method occurs. Furthermore, the switch can only go from SC to IV. In particular, the statistical model is constructed as:

$$Y_{ij} = \alpha + (\text{Randomization Factors})_i + u_{0i} + (\beta + u_{1i})t_{ij} + \beta_p(t_{ij} - t_{i,s})(1 - I_{x,i})I_{t_{ij} > t_{i,s}} + \left((\beta_{SC,x}t_{ij})I_{t_{ij} \leq t_{i,s}} + (\beta_{IV,x}(t_{ij} - t_{i,s}) + \beta_{SC,x}t_{i,s})I_{t_{ij} > t_{i,s}} \right)I_{x,i} + \epsilon_{ij}.$$

In this model, $t_{i,s}$ denotes the switching time for participant i after baseline; if a participant never switched in Study Period A of the study, then $t_{i,s}$ is defined as an arbitrarily large number (e.g., 100 with “year” as the unit). The parameter β_p denotes the effect of the change in administration method for participants in the placebo group. The variables $I_{t_{ij} \leq t_{i,s}}$ and $I_{t_{ij} > t_{i,s}}$ are indicator variables similarly defined as $I_{x,i}$. The annualized treatment benefit of crenezumab by SC is quantified by $\beta_{SC,x}$; the annualized treatment benefit of crenezumab by IV is quantified by $\beta_{IV,x}$. For model simplicity, up to 1 switch is assumed. The 95% CIs and p-values for estimates in $\beta_{SC,x}$ and $\beta_{IV,x}$ will be presented. The point estimates for the SC and IV treatment effect in the RR scale will also be presented.

- Analysis on each component of the API ADAD Composite Cognitive Test total score

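### The ARIA-H rule orders a lower dose that the documents do not define for either route, with conflicting count thresholds, and the SAP's supplementary SC-versus-IV model has no place for it

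*Protocol*

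**What the plan says.** **The rule.** Section 3.5.2.2 says "Participants who develop >8 ARIA-H cumulatively will receive a lower dose of the study drug", and a second threshold leads to a permanent stop. The count adds baseline and new findings. The Synopsis, Section 4.3.1.3 (Dosage Modification) and the footnotes to the Period A flowcharts, SC and IV (Appendices 1 to 4), repeat the rule. None of them gives an amount, a route or a schedule.

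**The regimens.** Section 3.1: "Crenezumab will be administered either SC (720 mg Q2W) or IV (60 mg/kg Q4W"). Section 4.3.1.2 fixes the SC administration: "The total volume of drug will be 2×2.0 mL (2×360 mg), administered in 2 injections". For IV, that section describes recalculating the dose only when body weight changes.

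**Movement between regimens.** Section 3.1, the Synopsis and SAP Section 1.2.1 make the move to IV optional and add that "once IV dosing in a given participant has occurred, it is not intended for a participant to switch back to the lower SC dose". For Period B, Section 3.2.1 lets participants keep their end-of-Period-A dose, listed as one of the same two regimens, or "switch to the higher dose of 60 mg/kg IV Q4W if they have not already switched". Section 3.2.2 leaves the choice of the higher dose to the participant after discussion.

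**ARIA-E.** For small asymptomatic findings the instruction in Section 3.5.2.2 is "Continue study drug at the same dose (i.e., 60 mg/kg crenezumab").

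**SAP.** The supplementary SC-versus-IV model in Section 5.3.5 uses route as the stand-in for dose, allows at most one switch, and states: "Furthermore, the switch can only go from SC to IV".

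**The concern.** The ARIA-H rule is mandatory and applies under the blind to active drug and placebo alike. A site whose participant falls in the reduction window must change the dose, but these documents do not tell it what to change to. Nor do they say whether the safety rule takes precedence over the stated intention not to go back from IV to SC.

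The conflicting thresholds mean that two sites with the same lesion count could act differently, depending on which page they read.

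On the analysis side, one supplementary model is meant to show whether the higher dose does more. If a participant's dose is reduced after the move to IV, the model still treats all later time as full IV dosing.

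**Working it through.** The power, alpha and sample size play no part here. The check compares the statements, with short arithmetic.

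**1. Which regimen is lower.** Inputs: 180 mg/mL (Section 4.3.1.1), two injections of 2.0 mL (Section 4.3.1.2), 60 mg/kg Q4W (Section 3.1), eligible weight 45 to 120 kg (Section 4.1.3).
- SC: 2 × 2.0 mL × 180 mg/mL = 720 mg, which reproduces the protocol's figure. Over 4 weeks: 2 × 720 = 1440 mg.
- IV over 4 weeks: 60 × 45 = 2700 mg to 60 × 120 = 7200 mg.
- Nominal ratio IV to SC: 2700/1440 = 1.9 to 7200/1440 = 5.0.

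SC is the lower of the two defined regimens at every eligible weight, and nothing is defined below it.

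**2. What the rule points to, by route.**

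| Current route | Lower regimen defined in the documents | Conflict |
|---|---|---|
| SC 720 mg Q2W | None | The footnotes to Appendices 1 and 2 apply the rule to SC dosing |
| IV 60 mg/kg Q4W | SC 720 mg Q2W only | Section 3.1, the Synopsis and SAP 1.2.1 say a return to SC is not intended |

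Section 4.3.1.3 is where a reader would expect the reduced dose. It only repeats the instruction: "Dose reduction: Participants who develop >8 ARIA-H cumulatively will receive a lower dose of the study drug".

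**3. The thresholds.** Sections 3.5.2.2 and 4.3.1.3 and the footnotes to Appendices 1, 2 and 4 reduce above 8 and stop above 10. The footnote to the flowchart for first IV dosing to Week 104 (Appendix 3, although its continuation pages carry an Appendix 4 header) reduces at 8 or more and stops at 10 or more.

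| Cumulative count | Most statements | Appendix 3 footnote |
|---|---|---|
| 8 | No change | Reduce |
| 9 | Reduce | Reduce |
| 10 | Reduce | Stop permanently |

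The window is thus 9 to 10 or 8 to 9. Entry allows up to 4 microhemorrhages. From a baseline of 4, the window is reached with 5 to 6 new findings (9 − 4, 10 − 4) or 4 to 5 (8 − 4, 9 − 4). From a baseline of 0 it takes 9 to 10 or 8 to 9.

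**4. The SAP model.** Let s be the switch time and r a later reduction time. After s, the treatment term in Section 5.3.5 for a crenezumab participant is

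β_SC,x · s + β_IV,x · (t − s),

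and for a placebo participant who switched it is β_p · (t − s). Neither changes at r. If the slope effect after reduction is β_R, the crenezumab term should be

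β_SC,x · s + β_IV,x · (r − s) + β_R · (t − r).

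The discrepancy is (β_IV,x − β_R) · (t − r), and it grows with time after the reduction. If the reduction is a return to SC, the one-way statement fails. If it is a smaller IV dose, that statement holds but route no longer stands for dose. In both cases the model is misspecified for that participant.

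**5. The primary model.** The model in SAP Section 5.3.3 has no route or dose term and compares arms as randomized, so nothing in step 4 enters it.

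**The case against.** There is a fair case that this is a drafting gap and not a contradiction.

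- **The intention in Section 3.1 is not a prohibition.** It follows a sentence about participants choosing their route, so it can be read as covering elective switching only. A specific safety rule would then take precedence. This stands: a reader might infer that the protocol forbids stepping down from IV, and the text does not say so.
- **A reduced dose may be defined elsewhere.** The rule never names SC as the lower dose, and Section 4.3.1.2 leaves IV preparation to the pharmacy manual, which is not among these documents. So one cannot conclude that no reduced dose exists. But neither Section 3.5.2.2 nor Section 4.3.1.3 points to the manual for it.
- **Section 4.3.1.3 sends such cases to the Medical Monitor.** This weakens any inference that sites would be left to improvise alone. It provides consultation but no dose.
- **The elective step-up is silent, not contradictory.** Sections 3.2.1 and 3.2.2 make no exception for someone under the rule, but a specific rule would ordinarily override a general option. It still deserves a sentence, because Section 4.5.6 does set conditions on restarting drug at the IV dose.
- **The Appendix 3 threshold may be a typographical slip.** Possibly, but that flowchart is the one sites follow after an early switch.
- **The SAP discloses its simplification and calls the model supplementary.** This stands, and it limits the statistical consequence. Section 5.6.1 also summarizes dose modifications and exposure by route.

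None of this gives a participant on SC a defined lower dose.

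**Conclusion.** The point holds in a limited form. As written, the dose-reduction rule cannot be carried out from these documents for participants on SC. For participants on IV it leads either to a regimen whose use after IV is said not to be intended or to a reduced IV dose that is not defined. The thresholds differ by one at each step, so counts of 8 and 10 receive different instructions depending on the page. The ARIA-E wording, which equates the same dose with 60 mg/kg, does not fit a participant on SC.

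The statistical effect is confined to the supplementary analysis in SAP Section 5.3.5. A reader might infer that the primary result is affected; the documents do not support that, because the primary model contains no route term.

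The number of participants in the window is not given. It is probably small, since even from the maximum permitted baseline several new findings are needed. The conclusion assumes that the pharmacy manual, not seen here, is not already the intended source of a reduced dose. If it is, a cross-reference would resolve the missing-dose part, but not the thresholds or the SAP model.

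**What to change.** **Protocol.** The sponsor's clinical team should reconcile the ARIA-H statements (Synopsis, Sections 3.5.2.2 and 4.3.1.3, footnotes to Appendices 1 to 4) with the dosing statements (Sections 3.1, 3.2.1, 3.2.2 and 4.3.1.2, and SAP Section 1.2.1). The rule should then be executable for each route and matching placebo, use one pair of thresholds throughout, and be consistent with the elective step-up to IV. The ARIA-E wording in the Synopsis and Section 3.5.2.2 should likewise be reconciled with SC dosing. Which dose or rule applies is a clinical decision, and none is proposed here.

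**SAP Section 5.3.5.** Do not count time after an ARIA-H dose reduction as full IV-dose time. Either end the IV segment at the reduction date, or add a separate time-varying segment after it in both arms, since the placebo arm has its own slope change at the switch. Align the one-way-switch statement with the reconciled rule; whether it needs to change depends on what the lower dose turns out to be.

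**Cost.** Wording changes in the protocol and its footnotes, and slightly more modelling in one supplementary analysis for what are probably few participants. With few of them, a separate post-reduction slope may be poorly estimated, which favours simply ending the segment. No visits or procedures are added.

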3.5.3 Pneumonia

In the RPCP of Phase II clinical trials in mild to moderate AD (Studies ABE4869g and ABE4955g) there was an imbalance in the rates of TLRTI (including PTs of pneumonia, LRTI, and bronchitis) driven by pneumonia. However, this imbalance was not replicated in the pooled data of the two large Phase III studies (BN29552 and BN29553) where the pneumonia cases were balanced between the crenezumab treatment and placebo arms (13 and 15 cases).

There is no clinical evidence of immunosuppression (e.g., effects on white blood cells or neutrophils; or pattern of infection type, e.g., opportunistic infections). In addition, no evidence of immunosuppression or of a lung toxicity effect has been observed in nonclinical studies.

Based on the currently available data, a causal relationship between the drug and events of pneumonia cannot be established or ruled out. Pneumonia is considered a potential risk to be monitored closely, and is added to this protocol as an adverse event of special interest.

Please refer to the latest Crenezumab Investigator's Brochure for further information on the incidence of pneumonia in all completed and ongoing studies.

3.5.3.1 Monitoring for Pneumonia

- It is of paramount importance to carefully document any pneumonia cases and other serious respiratory infections that occur in this study, by means of providing all relevant information required by the eCRF
- Participants with signs and/or symptoms suggestive of pneumonia (e.g., cough, fever, pleuritic chest pain) should undergo chest radiography for confirmation of diagnosis. Participants should be treated as per standard treatment care and any change to study drug should be considered within a benefit–risk assessment frame, and in agreement with the Medical Monitor.
- A chest X-ray is required under the following circumstances:
 - Serious and non-serious pneumonia
 - Serious and non-serious LRTIs
 - Serious upper respiratory tract infections
- In addition, whenever possible, additional relevant investigations should be conducted (e.g., WBC counts, pathogen identification by means of hemocultures, bronchoalveolar lavage)

